## 2.1 Sample size calculation

This is a phase 2 trial and the first Novo Nordisk trial of NNC0114-0006 in subjects with newly diagnosed T1DM. Therefore the knowledge on treatment effects and on the standard deviation of the primary endpoint is limited.

The statistical power calculations have been done under the following assumptions

- The primary endpoint is  $AUC_{0-4h}$  for a MMTT stimulated C-peptide concentration-time curve at week 54 relative to baseline, i.e.  $AUC_{0-4h, C-peptide, 54w} / AUC_{0-4h, C-peptide, baseline}$ . The primary endpoint will be log-transformed in the statistical analysis and this will be denoted  $\ln(AUC_{0-4h, C-peptide, \Delta 54w})$ . Thus,  $AUC_{0-4h, C-peptide, \Delta 54w}$  is the proportion of  $AUC_{C-peptide}$  that is preserved after 54 weeks relative to the level at baseline. E.g. a reduction of  $AUC_{C-peptide}$  of 35% corresponds to a preservation of 65% and value of the  $\ln(AUC_{0-4h, C-peptide, \Delta 54w})$  is  $\ln(0.65) = -0.431$ .
- The residual standard deviation of  $\ln(AUC_{0-4h, C-peptide, \Delta 54w})$  in the model described above may depend on the treatment. Based on the results of Herold et al. the standard deviation is assumed to be 1 in the placebo group and 0.5 in the group treated with NNC0114-0006 in combination with liraglutide.
- The expected preservation in the placebo treated patients is 65%, based on the results of Herold et al. who found a mean of 70% decline in  $AUC_{C-peptide}$  over a 24-months period. Assuming a linear decline, the mean 12-months decline would be 35%, i.e. a preservation of 65%. The statistical power calculations have been done assuming three levels of treatment effects for NNC0114-0006 in combination with liraglutide; a preservation of 85% and 95% and 98%, respectively.

[Table 2-1](#) shows the statistical power for the test of no treatment effect if the true mean preservation is 85%, 95% or 98% in the group treated with NNC0114-0006 in combination with liraglutide and 65% in the placebo group when the numbers of completers are 40, 60 or 80, respectively using a two-sided test and 5% level of significance. The rows corresponding to the chosen number of (completing) subjects are highlighted.

**Table 2–1 Power calculations**

True treatment effect (preservation)	N (completers per group)	Statistical power
85%	40	0.320
85%	60	0.451
85%	80	0.566
95%	40	0.561
95%	60	0.740
95%	80	0.854
98%	40	0.628
98%	60	0.804
98%	80	0.903

Assuming a preservation of 98% and a SD of 0.5 for NNC0114-0006 in combination with liraglutide and a preservation of 65% and a SD of 1 for placebo, then the power will be 80.4% with 60 subjects completing the trial in each of the two treatment arms.

## 2.2 Definition of analysis sets

The following analysis sets are defined in accordance with the ICH-E9 guidance:

- The full analysis set (FAS) will include all randomised subjects. Only in exceptional cases subjects may be excluded from the FAS. In such cases the reason for exclusion will be justified and documented. The statistical evaluation of the FAS will follow the intention-to-treat (ITT) principle and subjects will contribute to the evaluation ‘as randomised’.
- The PK analysis set will include all randomised subjects following the flowchart for the first 80 randomised subjects only, with at least one valid PK measurement. Subjects in the PK analysis set will contribute to the evaluation ‘as treated’.
- The safety analysis set will include all subjects receiving at least one dose of randomised treatment. Subjects in the safety analysis set will contribute to the evaluation ‘as treated’.

Analyses of efficacy and biomarker endpoints will be based on the FAS. Analyses of the PK endpoints will be based on the PK analysis set. Analyses of safety endpoints will be based on the safety analysis set.

Before the database is locked and ready for statistical analysis a review of all data will take place. Extreme values and outliers will be identified by the study group during programming and data review according to ICH-E9 using a fake randomisation. In addition, protocol deviations, which may potentially affect the results, will be identified and it will be evaluated if subjects and/or data should be excluded from analysis.

Obviously erroneous data points may be excluded from the analyses or re-analysed (in case of e.g. serum concentrations). The decision to re-analyse or exclude data points from the statistical analysis is the joint responsibility of the study group. Furthermore, the individual profiles for C-peptide and plasma glucose from the MMTT in the treatment phase will be examined prior to interim database lock to establish whether it is possible to calculate all endpoints. If samples that are important for the derivation of certain endpoints are missing, these endpoints will not be calculated and they will be excluded from the analysis. In these cases, the subjects, observations or endpoints to be excluded and the reason for their exclusion will be documented prior to interim database lock. Data that are not in scope for the interim database lock, including individual PK profiles, biomarkers, antibodies, and all data from the observation period may be examined after the interim database lock but before the full database lock. In cases where observations or endpoints are excluded from these data, it will be documented prior to the full database lock, and clearly stated if a decision was taken after randomisation code break. The subjects and observations excluded from analysis and the reason for exclusion will also be described in the clinical trial report.

The impact of protocol deviations and outliers may be investigated further in sensitivity analyses, if deemed relevant.

### 2.3 Primary endpoint

The primary endpoint is  $AUC_{0-4h}$  for a MMTT stimulated C-peptide concentration-time curve at week 54 relative to baseline:  $AUC_{0-4h, C-peptide, 54w} / AUC_{0-4h, C-peptide, baseline}$ .

The  $AUC_{0-4h}$  for MMTT stimulated C-peptide is derived at baseline and at 12, 24, 36, and 54 weeks and is denoted  $AUC_{0-4h, C-peptide, t}$ , where  $t$  is the time of the assessment. Thus,  $t=54$  weeks corresponds to the primary endpoint.

More specifically,  $AUC_{0-4h, C-peptide, t}$  at time 't' will be determined as the area from 0 to 4 hours under the C-peptide concentration profile after a MMTT using the trapezoidal method based on observed concentration values and actual measurement times. If the MMTT is stopped before 4 hours due to hyperglycaemia or hypoglycaemia, the last measured C-peptide concentration will be carried forward for calculation of the primary endpoint. If the MMTT is stopped before 4 hours it will most likely be due to hyperglycaemia as hypoglycaemia is not expected when a high amount of carbohydrates are ingested. Using last observation carried forward (LOCF) will result in an overestimated AUC since the C-peptide response is expected to be at the maximum level during hyperglycaemia. Furthermore, the risk of hyperglycaemia during MMTT will be higher in the placebo group if the active treatments have an effect on beta-cell preservation. Thus, LOCF is considered as a conservative approach. In case the MMTT is stopped before 4 hours for reasons that are not due to hyperglycaemia or hypoglycaemia, the remaining C-peptide concentrations will be set to  $lloq/2$ .

Let  $y_{it}$  denote the value of  $AUC_{0-4h, C-peptide, \Delta t}$  evaluated relative to baseline at time  $t$  for subject  $i$ , i.e.

$$y_{it} = \text{AUC}_{0-4h, \text{ C-peptide}, \Delta t} = \text{AUC}_{0-4h, \text{ C-peptide}, t} / \text{AUC}_{0-4h, \text{ C-peptide}, \text{ baseline}}$$

log of  $y_{it}$  will be analysed using an (MMRM) including all available assessments over time with treatment, stratum and sex as factors and  $\ln(\text{AUC}_{0-4h, \text{ C-peptide}, \text{ baseline}})$  and age at baseline as covariates (see [Table 2-2](#)). The interaction between all variables and visit (week) will be included in the model as fixed effects.

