Blood samples (11-point profile) will be collected 10 minutes prior to the meal (-10) at meal start (0), and at 15, 30, 60, 90, 120, 150, 180, 210 and 240 minutes after meal start. The blood samples will be assayed for C-peptide and plasma glucose. During the MMTT plasma glucose will be monitored on a validated plasma glucose instrument. If the glucose level exceeds 16.7 mmol/l (300 mg/dl) plasma ketones (betahydroxybutyrate) should be measured on a BG meter.

The subject is allowed to go to the toilet. The number of visits to the toilet should be limited. The subjects are allowed to drink water 2 hours after start of the MMTT. The amount of ingested water should be limited.

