#### **Documentation of the MMTT**

The following has to be recorded:

- Date of mixed meal tolerance test
- Was the subject fasting prior to intake of liquid meal (Y/N)
- Did the subject withhold the insulin treatment as required prior to the MMTT (Y/N)
- Was the last SMPG measurement at the site before start of the meal within the acceptable range (4.0-9.0 mmol/l)
- Code number(s) of the liquid meal
- Meal time. Actual time for the start and stop
- How much volume of the liquid meal was ingested (ml)
- Actual time points for the blood samples
- Was the MMTT stopped prematurely and reason for stopping

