### Sensitivity analyses of the primary endpoint

The following sensitivity analyses will be made

- To assess the impact of the endpoints calculated from MMTT that is stopped before 4 hours due to hyperglycaemia or hypoglycaemia, a sensitivity analysis will be performed excluding these endpoints.

- To assess the impact of the endpoints calculated from MMTT profile that includes imputed values, a sensitivity analysis will be performed excluding these endpoints.
- A sensitivity analysis will be performed excluding endpoints calculated from the MMTT, where the date of the MMTT is more than one day after the last liraglutide dosing.
- An analysis using last observation carried forward (LOCF) of the primary endpoint. The analysis will be made using a normal linear regression model for the log-transformed primary endpoint with treatment, stratum and sex as fixed factors and age and baseline value (log-transformed) as covariates.
- An analysis based on the subjects completing the treatment period (i.e. completing the visit at week 54). The analysis will be made using a normal linear regression model for the log-transformed primary endpoint with treatment, stratum and sex as fixed factors and age and baseline value (log-transformed) as covariates
- In case the assumption of equal variance-covariance between the treatments turns out not to be reasonable a sensitivity analysis will be added where the variance-covariance matrix for the repeated measurements for each subject will depend on treatment.

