### 3 Changes to the statistical analyses planned in the protocol

The below changes are made prior to the randomisation code break at the interim database lock:

- Various minor changes in wording done for clarification.
- The end of the treatment period is changed from the day before the visit at week 54 to the date of the visit at week 54, to ensure that the observations at end of treatment (Visit 63) gets assigned to the treatment period.
- Due to the change in assessments between the two flowcharts, it has been added that in case an endpoint is assessed at visits other than baseline, week 6, 12, 18, 24, 30, 36, 42, 48, 54, 65, and 80, values from the other visits will not be included in the MMRM.
- Subjects in the full analysis set will contribute 'as randomised' and not 'as treated' as per the ITT principle.
- The definition of the PK analysis set has been updated to include randomised subjects following the flowchart for the first 80 randomised subjects only.
- The following paragraph has been re-written to specify that decisions on data that are not in scope for the interim database lock can be taken after randomisation code break.
  - Furthermore, the individual profiles for C-peptide and plasma glucose from the MMTT in the treatment phase will be examined prior to interim database lock to establish whether it is possible to calculate all endpoints. If samples that are important for the derivation of certain endpoints are missing, these endpoints will not be calculated and they will be excluded from the analysis. In these cases, the subjects, observations or endpoints to be excluded and the reason for their exclusion will be documented prior to interim database lock. Data that are not in scope for the interim database lock, including individual PK profiles, biomarkers, antibodies and all data from the observation period may be examined after the interim database lock but before the full database lock. In cases where observations or endpoints are excluded from these data, it will be documented prior to the full database lock, and clearly stated if a decision was taken after randomisation code break.
- Specification on how to derive the primary endpoint in case the MMTT is stopped before 4 hours for reasons that are not due to hyperglycaemia or hypoglycaemia has been added:
  - In case the MMTT is stopped before 4 hours for reasons that are not due to hyperglycaemia or hypoglycaemia, the remaining C-peptide concentrations will be set to lloq/2.

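### C-peptide samples never drawn after a non-glycaemic early MMTT stop are set to lloq/2, which understates AUC0-4h in the primary analysis

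*SAP*

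**What the plan says.** SAP 2.3 (Primary endpoint) has two rules for an MMTT stopped before 4 hours. After a stop for hyper- or hypoglycaemia, the last measured C-peptide is carried forward, and the SAP argues that this is conservative. If the test stops "for reasons that are not due to hyperglycaemia or hypoglycaemia, the remaining C-peptide concentrations will be set to" lloq/2, no argument is given. SAP section 3 lists the second rule as an addition to the protocol analysis ("the remaining C-peptide concentrations will be set to lloq/2"), also without a reason. Protocol 17.3 contains no such rule.

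Other places bear on it:
- SAP 2.2: "If samples that are important for the derivation of certain endpoints are missing, these endpoints will not be calculated". The SAP does not say which rule prevails for a truncated test.
- SAP 2.3: the AUC "for MMTT stimulated C-peptide is derived at baseline and at 12, 24, 36, and 54 weeks", so the rule also reaches the baseline denominator.
- SAP 2.3, sensitivity analyses: for "the endpoints calculated from MMTT profile that includes imputed values, a sensitivity analysis will be performed excluding these endpoints". The primary analysis keeps them.
- Protocol 8.3.1 samples at 10 min before the meal, at meal start, and "at 15, 30, 60, 90, 120, 150, 180, 210 and 240 minutes after meal start". It also records "Was the MMTT stopped prematurely and reason for stopping".

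**The concern.** Half the LLOQ is a convention for a sample that was assayed and found unquantifiable. Here no sample exists. A subject who leaves at 120 min with a C-peptide of, say, 0.5 nmol/l is recorded as having almost none from 150 min on. The resulting AUC0-4h enters the log ratio analysed by the primary MMRM, and so its estimate, confidence interval and p-value.

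The bias has no fixed direction between arms. Stops in an active arm work against it, stops in placebo favour every active arm, and all pairwise comparisons are reported (SAP section 2). At baseline the error reverses: the denominator is understated and that subject's later ratios are inflated.

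SAP 2.4.1.1 derives the other MMTT AUC endpoints in the same way, so the week-80 C-peptide AUC inherits the rule. Read literally, the glucose AUCs would too.

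**Working it through.** **1. Plan's own figure.** Inputs from SAP 2.1: preservation 98% and SD 0.5 (combination), "a preservation of 65% and a SD of 1 for placebo, then the power will be 80.4% with 60 subjects" completing per arm, two-sided 5%.

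- Planned effect: ln(0.98/0.65) = 0.411
- Contrast SE: √((0.5² + 1²)/60) = 0.144
- Power: 0.803 by noncentral t with Satterthwaite df, 0.812 by normal approximation; stated 0.804. The inputs are read correctly.

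**2. Exact result for a flat profile.** With true level c, last sample at s minutes, later values v = lloq/2 and 30-minute spacing, the trapezoidal area is c·s + 30·(c+v)/2 + v·(240−s−30). Divided by 240c:

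share of true AUC = w + (1−w)·v/c, with w = (s+15)/240.

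This gives w = 0.3125, 0.4375, 0.5625, 0.6875, 0.8125 and 0.9375 for s = 60, 90, 120, 150, 180 and 210. Example with c = 0.1 and LLOQ 0.05 nmol/l at 120 min: 0.5625 + 0.4375 × 0.25 = 0.672, ln = −0.40.

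**3. Range over assumed profiles.** LLOQ, peaks and shapes are not in the documents. Assumed, as fractions of peak at 0, 15, 30, 60, 90, 120, 150, 180, 210, 240 min:
- flat: all 1
- A: .45 .50 .62 .88 1 .97 .90 .80 .70 .62
- B: .40 .43 .52 .75 .93 1 .96 .88 .78 .70

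Peaks are 0.1, 0.2, 0.5 and 1.0 nmol/l; LLOQ is 0.003 and 0.05 nmol/l (24 combinations).

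| Last sample (min) | Recorded/true AUC, lloq/2 | ln shift | Shift exceeds 0.411 | Recorded/true AUC, carry-forward |
|---|---|---|---|---|
| 60 | 0.230–0.484 | −1.47 to −0.72 | 24 of 24 | 0.878–1.025 |
| 90 | 0.376–0.600 | −0.98 to −0.51 | 24 of 24 | 1.000–1.128 |
| 120 | 0.533–0.713 | −0.63 to −0.34 | 21 of 24 | 1.000–1.107 |
| 150 | 0.684–0.814 | −0.38 to −0.20 | 0 of 24 | 1.000–1.069 |
| 180 | 0.813–0.901 | −0.21 to −0.10 | 0 of 24 | 1.000–1.030 |
| 210 | 0.938–0.971 | −0.06 to −0.03 | 0 of 24 | 1.000–1.006 |

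The counts show how robust the comparison is to the assumptions; they are not probabilities. Adding LLOQ 0.1 nmol/l gives 35, 33, 27 and 0 of 36 at 60, 90, 120 and 150 min. In its extreme case, LLOQ equal to a peak of 0.1, the upper ends rise to 70% at 60 min and 85% at 120 min.

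**4. Trial level.** One affected subject among 60 moves the arm mean by |ln share|/60:
- 120 min: 0.006 to 0.011, or 1–3% of 0.411 and 4–7% of the SE
- 60 min: 0.012 to 0.025, or 3–6% of 0.411 and 8–17% of the SE

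Illustration with three of 60 combination-arm values recorded at 0.56 of truth: the effect becomes 0.411 + (3/60)·ln 0.56 = 0.382, and power falls from 0.812 to 0.753. If those three are missing instead, the SE is √(1/60 + 0.25/57) = 0.145 and power is 0.808 (both by normal approximation).

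**5. Baseline.** For a flat profile stopped at 120 min with LLOQ near zero, the raw ratio is multiplied by 1/0.5625 = 1.78.

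**The case against.** The strongest reply is that trial-level harm is not shown. The documents give no count of non-glycaemic stops and suggest few. SAP 2.3 expects early stops to be mostly hyperglycaemic, the stopping provisions in Protocol 8.3.1 and Amendment 2 name only glycaemic reasons, and Amendment 2 (section 8.1.6) foresees re-sampling of the MMTT. The planned effect is a difference between arm means, so setting one subject's error beside it can mislead. All of this stands, and it is why step 4 gives the arm-level figures.

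The rule was fixed before code break, and the sensitivity analysis excluding imputed profiles will expose its influence. That also stands, but the primary estimate is left as it is, and the exclusion removes carried-forward profiles along with the lloq/2 ones.

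At baseline, the MMRM adjusts for log baseline AUC, so an error d in log baseline leaves about b·d in the adjusted outcome, where b is the slope of later log AUC on log baseline. The 1.78 applies to the raw ratio only. Baseline tests also precede randomisation, so they add noise rather than expected treatment bias. Truncated ones should be rare, because eligibility uses the highest of the 11 Visit 2 samples.

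Lastly, treating the value as missing assumes missingness at random. That may fail if drug-related symptoms end the test; Protocol 18.1 names gastrointestinal events as the most common with liraglutide, mostly early in treatment. The choice between missing and carry-forward is therefore open to debate. Neither alternative makes lloq/2 a sound primary value.

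**Conclusion.** The concern holds. As written, the rule puts an artificially low AUC0-4h into the primary analysis for any test stopped early for a non-glycaemic reason, unless true later C-peptide was already at or below lloq/2. For the affected subject the error is material for stops up to about 120 min, where it is comparable to the planned effect but not always larger, and it is small by 210 min.

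The trial-level effect is unknown and probably modest. Its direction depends on the arm in which the stops occur, so the rule cannot be defended as conservative. The sizes rest on the assumed LLOQ, peaks and shapes; the direction at the affected visit needs only later values above lloq/2. This should be fixed.

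**What to change.** Change a few SAP sentences before code break:

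- Delete the lloq/2 sentence from SAP 2.3 and its entry in section 3. For a post-baseline MMTT stopped early for a non-glycaemic reason, leave AUC0-4h uncalculated, in line with SAP 2.2, and let the MMRM treat that visit as missing. Keep AUC0-2h where it is fully observed.
- State a separate rule for a truncated baseline MMTT, since a missing baseline drops the subject from the model. Within-profile carry-forward, already used for glycaemic stops, is one option.
- Say which of SAP 2.2 and 2.3 prevails for truncated tests, and apply the same rule to the week-80 and glucose AUCs.
- Keep lloq/2 and within-profile carry-forward for post-baseline non-glycaemic stops as sensitivity analyses.
- Report early stops by arm, visit, stop time and reason; the reason is already collected.

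No new data are needed. The cost is a few missing values, including some nearly complete profiles (stops at 180 to 210 min, where lloq/2 loses about 3–19%), and reliance on missing at random.

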**Table 2-2 Model terms for the statistical model for the primary endpoint**

Model term	Description
$\ln(y_{it})$	dependent variable, subject i, time t
$\ln(\text{AUC}_{0-4h, \text{ C-peptide}, \text{ baseline}})$	fixed effect covariate with a visit dependent coefficient
Visit	fixed effect factor corresponding to time t=12w, 24w, 36w, 54w
Treatment	fixed effect interaction term between treatment and visit (i.e. the treatment effect is not assumed the same for all visits), with treatment as a factor with 4 levels: NNC0114-0006 in combination with liraglutide, NNC0114-0006, liraglutide and placebo
Stratum	fixed effect interaction term between stratum and visit, with stratum as a factor with two levels according to non-fasting max C-peptide measurement during MMTT at Visit 2: 0.2-0.6 nmol/l and >0.6 nmol/l
Age	fixed effect covariate with a visit dependent coefficient
Sex	fixed effect interaction term between sex and visit

The variance-covariance matrix for the repeated measurements for each subject will be unstructured.

From the model, least square means (LSMeans) for each treatment group at selected time points, including week 54 will be estimated, and mean differences between treatment groups in log-transformed  $\text{AUC}_{0-4h, \text{ C-peptide}, \Delta t}$  at these time points will be estimated. These estimates will be back-transformed to the original scale to represent treatment (geometric) means and treatment (geometric mean) ratios with 95% CIs.

The primary endpoint will be summarised using descriptive statistics and presented graphically.

